#### **Primary Outcomes**

The primary objectives of this study are:

1. To investigate possible mechanisms of weight loss with exenatide treatment
2. To determine long-term patterns of weight loss among individuals who have robust (>5%) early weight loss with exenatide

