#### **Secondary Outcomes**

Our secondary objective is to identify metabolic characteristics that predict robust response to exenatide treatment.

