#### *Outcome measurements:*

*Weight:* We will compare the duration and magnitude of weight loss among exenatide responders with the

duration and magnitude of weight loss among subjects assigned to placebo with a calorie-restricted diet over 52 weeks. We will also compare changes in weight at 3 and 6 months after the cessation of exenatide treatment or diet. Weight loss will be correlated to baseline BMI.

**Body composition:** Baseline body composition may predict response to exenatide treatment, and weight loss with exenatide may be associated with decreased fat versus lean body mass compared to diet-induced weight loss. We will compare the effect of exenatide treatment versus caloric reduction on body composition over 52 weeks using bioelectrical impedance analysis (BIA) and by measuring waist circumference.

**Resting energy expenditure (REE):** Our initial data suggest that exenatide may blunt the decrease in resting energy expenditure that is typically associated with diet-induced weight loss. We will measure resting energy expenditure (REE) via indirect calorimetry at baseline, at weeks 12, 24, and 52, and after 5%, 10%, 15% weight loss is achieved, and at additional 5% weight loss timepoints, as applicable (i.e., 20%, 25%, etc).

**Mixed meal test:** Exenatide may improve beta cell function and lower postprandial triglycerides in nondiabetic individuals. Measurement of fasting insulin and triglyceride levels does not capture these effects. We will administer a mixed liquid meal (Boost) and measure serial postprandial insulin, , and triglyceride levels. Subjects will have a mixed meal test at baseline, and at weeks 12, 24, and 52.

**Thermic effect of food:** Exenatide treatment may result in an increase in the thermic effect of food, which could explain, at least in part, why we did not see a significant reduction in energy expenditure among exenatide high responders in our initial study. We will measure the thermic effect of food using indirect calorimetry following the mixed meal challenge. Energy expenditure will be measured for 15-20 minutes every hour for four hours after the mixed meal challenge. The thermic effect of food will be measured in a subset of subjects at baseline, and at weeks 12, 24, and 52.

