An important clinical consideration with all pharmacotherapeutic agents, and especially those that are associated with weight loss, is identifying as early as possible individuals who do and do not respond to treatment. In our recently completed study of 41 overweight and obese women without diabetes, we found that exenatide treatment was associated with a significant decrease in weight, BMI, and waist circumference compared to placebo. There was also a trend towards decreased sleep latency (how long it takes to fall asleep) with exenatide treatment compared to placebo. We did not find any significant differences in blood pressure, body composition, lipid parameters, leptin levels, insulin levels or resting energy expenditure when we compared exenatide treatment to placebo overall, but we did note that a few subjects had dramatic changes in fasting insulin, glucose, leptin, or triglyceride levels.

In our initial study we also made the interesting observation that exenatide high responders did not have a significant decrease in resting energy expenditure (REE) despite an average 8% weight loss. Whereas diet-induced weight loss of this magnitude has been shown to result in a decrease in resting energy expenditure, which facilitates weight regain, our data suggest that exenatide may blunt this decrease in REE and thereby permit ongoing weight loss. In the present study, we will compare resting energy expenditure as well as the thermic effect of food among exenatide high responders, nonresponders, and subjects with diet-induced weight loss.

Another mechanism of weight loss may be a change in leptin sensitivity. Serum leptin levels have been shown to fall in obese individuals with diet-induced weight loss (Crujeiras 2010), and in our initial study, we found that high responders had a significant decrease in leptin levels compared to nonresponders. While this decrease may reflect weight loss, it may also reflect sensitization to leptin. Furthermore, measurement of total serum leptin levels may not be the best tool for assessing leptin sensitivity. In a cohort of lean males fasted for 72 hours, leptin levels fell while levels of the soluble leptin receptor increased (Chan et al, 2002). Measurement of both total leptin and soluble leptin receptor levels, and in turn calculation of the free leptin index, can provide more a more detailed assessment of leptin resistance.

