The placebo arm will be used to study weight-loss induced metabolic changes that are independent of exenatide. Because the subjects in the placebo/dietary intervention arm serve as a weight-loss comparison group, these subjects will be dropped from the study at 12 weeks if they do not lose 5% of their body weight. Subjects in the exenatide treatment arm will be characterized as “non-responders” (<5% weight loss) or “responders” (≥5% weight loss) based on weight loss at 12 weeks. Data from our previous exenatide study in non-diabetic obese women shows that 12 weeks provides a reasonable timeframe to differentiate “non-responders” and “responders.” Because this study focuses only on the characteristics of exenatide responders, subjects in the exenatide treatment arm with less than 5% weight loss at 12 weeks will be dropped from the study. Exenatide “responders” will continue treatment for 52 weeks to assess the magnitude and duration of weight loss in this subgroup. These subjects will also participate in 3-month and 6-month follow-up visits to assess weight changes post-treatment. Subjects in the dietary intervention arm will continue study participation for up to 52 weeks if they demonstrate ongoing weight loss and then attend 3-month and 6-month follow-up visits after returning to *ad-lib* eating.

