**Study duration:**

All subjects randomized to exenatide treatment will continue participation for 12 weeks. At 12 weeks, subjects who are high responders will continue participation for 52 weeks plus followup visits at 3 and 6 months. Exenatide high responders will remain in the study even if weight loss plateaus or if there is weight regain. Exenatide nonresponders will discontinue participation after 12 weeks.

Subjects in the placebo/diet intervention arm will discontinue participation if they fail to lose 5% of their body weight after 12 weeks or 10% of their body weight after 24 weeks. Subjects who demonstrate ongoing weight loss will continue placebo/dietary intervention for up to 52 weeks, plus follow-up visits at 3 and 6 months. Metabolic monitoring will occur when subjects have lost 5% and 10% of their body weight.

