To estimate the number and shape of the weight loss trajectories, we will use a mixture modeling technique of the longitudinal data of monthly weights for each subject. We will first plot the data for each subject over time. The graphs will allow us to have some understanding of the shape of the observed trajectories, and how the curves cluster. We will assume that the number of clusters ranges from one to six, but we expect the optimal estimate of the number of clusters is three or four, as described above, with the largest cluster consisting of trajectory of shape T1. The marginal density of a subject having weight measurement at a particular time point is modeled as a function of the product of two densities: the probability of the weight measurement belonging to a particular group, and the probability of observing such a measurement conditioning on the particular group. The first probability is modeled using a generalized logit model since the outcome is categorical (from 1 to 6 categories/types of trajectories), and the second probability is a polynomial linear regression of the weight measurement as a function of time (linear, quadratic, cubic). To select the optimal number of trajectories, we will compare the Bayesian Information Criteria (BIC) value from the six models (corresponding to 1 to 6 types of trajectories). The algorithm and the SAS macro for this type of modeling has been published (Jones 2007). We will repeat the modeling technique above for group B in order to assess the number and shapes of the trajectories in this group.

For aim 2, we will first create a binary outcome variable. The outcome is 1 if the weight loss difference between 12-week and 52-week is at least 1 kg; otherwise, it is 0. We will perform multivariable logistic regression to assess the association between metabolic parameters and this outcome. We consider the association to be statistically significant if the p-value is less than 0.05, and the overall model c-statistic is above 0.8. Once these metabolic parameters have been identified and quantified, we will also use the result from the trajectory analysis (aim 1) to assess the distribution of the metabolic parameters across different trajectories. We will model the likelihood of falling into a particular trajectory as a function of metabolic parameters (i.e. the change in a particular metabolic parameter may affect a certain trajectory but not all trajectories of weight loss).

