**Sample size calculation:**

Based on published literature describing weight loss with exenatide treatment among individuals with type 2 diabetes, we hypothesize that responders will stratify into a plateau group and a continued weight loss group by 52 weeks of treatment. The sample size is based on the difference between two differences of weight. The first difference is the weight difference between week 12 and week 52 for the exenatide group (group A), and the second difference is the difference between week 12 and week 52 for the diet-induced group (group B). The difference in weight loss between these two groups is hypothesized to be 1 kg (i.e. the exenatide group between week 12 and 52 loses on the average 1 kg more than group B). The common standard deviation of the distribution of the weight loss difference is 1.2 kg. We plan to enroll 150 subjects in group A and 36 in group B. Given an expected dropout rate of 25% from the screening visit, we will screen 200 for group A, and 50 for group B. At 12 weeks, we expect that 30% of group A will be high responders (50 subjects). At 52 weeks, we expect the dropout rate to be 25% for group A and 50% for group B. Thus we will have 38 subjects left for group A, and 18 for group B for final data analysis. Given this sample size, we will still have a power of 0.83 to detect the difference of 1kg.

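### The metabolic-predictor models do not match the secondary objective on early response, and the exenatide-versus-diet coefficient difference is read as a possible drug effect without an interval

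*Combined protocol and SAP*

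**What the plan says.** **The objective.** Under Secondary Outcomes: "Our secondary objective is to identify metabolic characteristics that predict robust response to exenatide treatment". Under Primary Outcomes, robust is tied to early loss: "To determine long-term patterns of weight loss among individuals who have robust (>5%) early weight loss with exenatide". The Rationale for study design classifies exenatide women as responders or nonresponders by weight loss at week 12: "Data from our previous exenatide study in non-diabetic obese women shows that 12 weeks provides a reasonable timeframe to differentiate" the two. Under Study duration: "Exenatide nonresponders will discontinue participation after 12 weeks".

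**The models.** Statistical methods has two strands.
- Trajectory mixture models for women with robust weight loss, with segments starting at week 12.
- For aim 2, a multivariable logistic regression on metabolic parameters with this outcome: "The outcome is 1 if the weight loss difference between 12-week and 52-week is at least 1 kg; otherwise, it is 0". A model of trajectory membership on metabolic parameters follows.

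**The group comparison.** The models are then repeated in the diet group (B). The difference between the coefficients in the exenatide group (A) and in B is said to suggest a possible exenatide effect. No test, standard error or interval is mentioned.

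**Retention.** Under Study duration and the week 24 visit, diet women who have not lost 10% by week 24 leave. Exenatide responders stay even if their weight plateaus or rises.

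**The concern.** There are two separate problems.

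1. Finding what predicts response requires comparing women who respond with women who do not, or modelling week-12 loss across all of them. The specified models contain only women who have already responded. They show what goes with further loss after week 12, which is a different question. Followed as written, the section cannot answer the secondary objective, although the baseline markers are collected in every woman.

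2. Coefficients fitted separately in two small groups will differ by chance. Without an interval the reader cannot tell how much. The groups are also formed after randomisation and retained under different rules, so even a precisely estimated difference would not be a randomised effect of exenatide. The risk is that a chance or selection difference is taken for a drug mechanism.

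**Working it through.** **1. Objective against model**

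| | Secondary objective | Specified models |
|---|---|---|
| Outcome | More than 5% early loss, classified at week 12 | At least 1 kg difference, week 12 to 52; trajectory membership |
| Women needed or used | Responders and nonresponders | Responders only |
| Planned exenatide women | 150 | 38 |

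The 38 comes from the Sample size calculation, which assumes 30% response. With the response rate of about 60% in the Rationale for study design, applied to all 150 (an assumption), it is 150 × 0.60 × 0.75 ≈ 68. Either way the nonresponders are absent.

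The text does not say which objective aim 2 refers to. If it means the secondary objective, the outcome does not match. If it means a primary objective, the secondary objective has no model of its own. The gap remains on both readings.

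**2. The plan's own power figure**

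Inputs from the Sample size calculation: 38 and 18 women, difference 1 kg, SD 1.2 kg; two-sided 5% assumed.
- SE = 1.2 × sqrt(1/38 + 1/18) = 0.343
- 1/0.343 − 1.96 ≈ 0.95, so power = 0.83 (0.816 with the t distribution)

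The stated 0.83 reproduces. It concerns a difference in mean weight change, and covers neither week-12 response nor a difference in regression coefficients.

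**3. Chance variation in the A–B coefficient difference**

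Assumptions: one standardised marker, no true difference, event share p in both groups (the plan gives none; 50% is the most favourable).
- SE of the log ratio of odds ratios = sqrt(1/(38·p·(1−p)) + 1/(18·p·(1−p)))
- p = 0.5: SE = 0.572; 95% chance range exp(±1.96 × 0.572) = 0.33 to 3.07
- p = 0.3 or 0.7: SE = 0.624; range 0.29 to 3.40
- Chance of a ratio at least two-fold in either direction at p = 0.5: 2 × (1 − Φ(0.693/0.572)) = 23%

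This large-sample formula is too narrow with 18 women in one group. Simulating 5,000 pairs of logistic fits at p = 0.5 gives 0.21 to 4.66 in one run and 0.21 to 4.99 in another, with a two-fold ratio by chance in 32% to 33%.

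**4. Larger groups**

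The Rationale for study design gives 84 + 24 = 108 exenatide and 28 + 10 = 38 placebo enrolled, if those counts add. Two extensions at 2:1, with 60% response and 25% later dropout in A and 50% dropout in B:
- Stop at 150 in A: 42 more there adds 21 to B, giving 59. Analysed: about 68 and 59 × 0.50 = 29.5. Formula range 0.42 to 2.37; simulated 0.36 to 2.91, with a two-fold ratio by chance in 16%.
- Reach the stated goal of 250: 104 more gives about 177 and 73. Analysed: about 80 and 36. Formula range 0.46 to 2.20, with a two-fold ratio by chance in 8%.

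The current allocation figure is not shown, so these sizes are assumptions.

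**5. Is a week-12 analysis feasible?**

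Week 0 of the visit schedule lists seven fasting markers for every woman; BMI and bioimpedance body composition make nine predictors. With Bonferroni over nine (z = 2.773) and 80% power (0.842), the detectable correlation with week-12 percent loss is tanh(3.615/sqrt(n − 3)):
- n = 150: 0.29
- n = 112 (25% without a week-12 weight, an assumption): 0.33

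If the other predictors explain 30% of a marker's variance (an assumption), these become 0.34 and 0.39.

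**The case against.** **The plan does contain a metabolic-predictor analysis.** It is labelled aim 2, and its outcome fits the sample-size hypothesis that "responders will stratify into a plateau group and a continued weight loss group by 52 weeks of treatment". This stands. A reader might infer that the secondary objective has no analysis at all, or that the 1 kg outcome is a mistake. The documents support neither. The defect is a mismatch between objective and outcome, and the 1 kg model can stay for the question it answers.

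**Other sections touch on response.** Outcome measurements says "Weight loss will be correlated to baseline BMI", and raises baseline body composition and early appetite and nausea scores as possible predictors. The background section intends to "compare resting energy expenditure as well as the thermic effect of food among exenatide high responders, nonresponders, and subjects with diet-induced weight loss". These are relevant intentions, but none specifies a model of response on the metabolic markers.

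**The wording on group differences is hedged, and no decision rule is attached to it.** True. The plan does not claim an established drug effect, and standard errors from the separate fits would yield an interval directly. What remains is that no interval is called for, and the hedge does not tell a reader how large a chance difference can be.

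**A pooled interaction model is not essential.** Agreed. For the 1 kg model, a fully interacted model gives the same coefficient differences as separate fits. It also cannot simply replace the trajectory-membership models, because the number and shape of classes are estimated separately in each group.

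**Conclusion.** The concern holds on both parts.

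The mismatch follows from the text alone and needs no numerical assumption: the specified metabolic models are confined to responders and to weight change after week 12, while the objective concerns early response.

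For the group comparison, the 38 versus 18 in the plan implies a chance range of roughly 0.2 to 5 for the ratio of odds ratios per SD, and a two-fold ratio by chance in about a third of comparisons. This assumes one marker, 50% events and no true difference. The planned models are multivariable, so these single-marker figures do not describe them exactly. Larger groups would narrow the range, by an amount that depends on enrolment.

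A reader might infer that adding a test would turn the coefficient difference into an effect of exenatide. It would not. Both groups are selected on weight loss after randomisation, and the week 24 rule applies to diet women only. That rule bears directly on the week 12 to 52 outcome.

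**What to change.** 1. **Week-12 response.** Keep the current models for later weight loss. For the secondary objective, add one analysis in all women randomised to exenatide: regress week-12 percent weight loss on a short prespecified list of week-0 characteristics already collected (for example the fasting markers, BMI and bioimpedance), with loss of at least 5% as a supportive outcome. State the multiplicity approach. Handle missing week-12 weights using the earlier weights, for example by multiple imputation with weeks 0, 2, 4 and 8, and show complete cases as a sensitivity analysis.

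2. **Group comparison.** For the 1 kg logistic model, report the A–B coefficient difference with a 95% confidence interval, from the separate fits' standard errors or equivalently a group-by-marker interaction. A small-sample method such as penalised likelihood is preferable. Compare the trajectory-membership models descriptively only.

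3. **Wording.** Describe A–B differences as exploratory associations among responders selected after randomisation under different retention rules, not as an effect of exenatide.

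**Cost.** Plan wording and modest analysis time; no new visits or assays. Fewer markers will be declared significant. The week-12 model describes who loses weight on exenatide, not who benefits relative to placebo. The A–B interval will be wide: at 38 versus 18 and 50% events, 80% power needs a ratio of odds ratios near exp(2.80 × 0.572) ≈ 5.0 by the large-sample formula, which is probably optimistic. The gain there is an honest interval and label.

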**Inclusion/Exclusion Criteria****Inclusion Criteria**

1. Females age 18-70
2. BMI 28-50 kg/m^2
3. Stable weight (< 3 kg weight gain or loss within 6 months of screening visit)
4. Ability to give informed consent and follow verbal and written instructions in English

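### Aim 2 splits the week 12-to-52 weight change at an unjustified 1 kg, less than one planning SD, so the binary outcome sorts women imperfectly and discards information from a small sample

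*Combined protocol and SAP*

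**What the plan says.** Under Statistical methods, aim 2 defines its outcome as follows: "The outcome is 1 if the weight loss difference between 12-week and 52-week is at least 1 kg; otherwise, it is 0". A multivariable logistic regression then relates metabolic parameters to it. Success needs both a p-value below 0.05 and a model c-statistic above 0.8. The parameters found in this way are next compared across the weight trajectories from aim 1, and trajectory membership is modelled on metabolic parameters. The models are repeated in the diet group (group B).

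The section does not say why 1 kg was chosen. The same figure appears in the Sample size calculation, where it is a difference between group means: "The difference in weight loss between these two groups is hypothesized to be 1 kg". The spread is given there too: "The common standard deviation of the distribution of the weight loss difference is 1.2 kg". The expected numbers are also stated: "Thus we will have 38 subjects left for group A, and 18 for group B for final data analysis".

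**The concern.** A mean difference of 1 kg between arms is a group-level planning value. It gives no basis for classifying an individual woman. Used as an individual cut, it rests on two weights 40 weeks apart and is smaller than one SD of the change being cut. Women with no real further loss can then be coded 1, and women with a modest real loss can be coded 0.

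Such misclassification weakens the association between any metabolic parameter and the outcome, and it limits the c-statistic that can be reached. A parameter could therefore fail the plan's criterion because of how the outcome was built and not because it is uninformative. Dichotomising also treats a 1.1 kg loss and a 6 kg loss as the same result, which is costly in a sample of this size.

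**Working it through.** **Inputs from the plan.** Cut 1 kg (Statistical methods). SD of the week 12-to-52 change 1.2 kg, between-arm difference 1 kg, and 38 and 18 women analysed (Sample size calculation). c-statistic criterion above 0.8 (Statistical methods).

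**Assumptions.** Individual changes are normally distributed. Loss is counted as positive. The true losses of 0, 2 and 3 kg and the equal mix are illustrative.

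**1. The plan's own figure.** SE = 1.2 × √(1/38 + 1/18) = 0.343. Then 1/0.343 − 1.96 = 0.95, and Φ(0.95) = 0.83. The stated power of 0.83 reproduces (two-sided 5%, normal approximation; 0.816 with the t distribution). So 1.2 kg is the SD on which the plan rests.

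**2. Misclassification, with all of the 1.2 kg taken as fluctuation.**
- True change 0: P(observed loss ≥ 1) = 1 − Φ(1/1.2) = 1 − Φ(0.833) = 0.202.
- True loss 2 kg: P(observed loss < 1) = Φ((1 − 2)/1.2) = Φ(−0.833) = 0.202.
- True loss 3 kg: P(observed loss < 1) = Φ(−2/1.2) = 0.048.

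**3. Ceiling on the c-statistic.** Take an equal mix of true 0 and true 2 kg, and a marker that identifies true class perfectly but carries no information on the fluctuation. Half of the women are coded 1. Among those coded 1, the share with the marker is 0.5 × 0.798 / 0.5 = 0.798. Among those coded 0, the share without it is also 0.798. For a binary marker, c = (0.798 + 0.798)/2 = 0.798, just below the criterion. With a true further loss of 3 kg instead of 2, the ceiling rises to 0.88.

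**4. How far the SD matters.** The 1.2 kg is the spread across women, so it already contains true differences between them. An equal mix of 0 and 2 kg has a between-class variance of 1 kg². With a fluctuation SD of 1.2, the total SD would be √(1.44 + 1) = 1.56 kg, more than the plan's value. If the total is held at 1.2 kg, the fluctuation SD is √(1.44 − 1) = 0.66 kg, the error rate is 1 − Φ(1/0.66) = 0.066, and the ceiling is 0.93. In the other direction, an assumed fluctuation SD of 2 or 3 kg codes 31% or 37% of women with no true change as 1.

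| Fluctuation SD (kg) | True 0 coded 1 | True 2 kg coded 0 | Ceiling, 0 and 2 kg mix |
|---|---|---|---|
| 0.66 (total held at 1.2) | 6.6% | 6.6% | 0.93 |
| 1.2 (plan's SD, upper bound) | 20% | 20% | 0.80 |
| 2 (assumed) | 31% | 31% | 0.69 |
| 3 (assumed) | 37% | 37% | 0.63 |

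**5. Events.** In group B, with mean change 0 (assumed) and SD 1.2: 18 × 0.202 = 3.6, about 4 events. In group A, with mean loss 1 kg (assumed): 38 × 0.5 = 19 events. Four events cannot support a multivariable logistic model.

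**The case against.** The best defence is that the plan has a second route. After the logistic model it relates metabolic parameters to trajectory membership, which comes from monthly weights and uses no 1 kg cut. This stands as mitigation. It does not remove the problem, because the text places that work after the parameters have been identified, and the logistic step does the identifying.

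It is also fair to say that 20% is an upper bound under the plan's values, as step 4 shows. The documents do not separate within-woman fluctuation from true differences.

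Some stronger readings are tempting, but the documents do not support them.

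- **That the plan contradicts itself.** The entry criterion reads "Stable weight (< 3 kg weight gain or loss within 6 months of screening visit", and 1 kg over 40 weeks (0.65 kg per 26 weeks) lies well inside that band. But this criterion screens weight history before enrolment. It does not define a plateau on treatment and says nothing of the spread of ordinary change. Reading it as two SDs (SD 1.5 kg, 25% misclassified) is a construction, and 1.5 kg exceeds the plan's total SD.
- **That the outcome cannot separate the groups.** About 80% of women with no true change are coded correctly at SD 1.2 kg, and about 95% of those with a true 3 kg loss. That is imperfect separation, not failure.
- **That aim 2 exists to split plateau from continued loss.** The sample size section does hypothesise that "responders will stratify into a plateau group and a continued weight loss group by 52 weeks of treatment", but the aim-2 text does not link its outcome to that sentence. The link is a reasonable inference and no more.
- **That a kilogram cut is out of line with all other thresholds.** The 5%, 10% and 15% response thresholds are percentages, but the stability criterion and the planning difference are in kilograms.

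**Conclusion.** The concern holds as a moderate point about the choice of analysis. The 1 kg cut is unexplained, lies below the plan's 1.2 kg SD, and turns a continuous measurement into a binary one without need. Up to about 20% of women with no true change, and the same share with a true 2 kg loss, would be misclassified under the plan's values. In an equal mix of those two groups the best attainable c-statistic is then about 0.80.

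These sizes depend on normality, the assumed true losses and mix, and the reading of the SD. The plausible range is wide: the ceiling is 0.93 if part of the SD is true difference, and lower than 0.80 if fluctuation exceeds 1.2 kg. The event counts use the planned 38 and 18. The Rationale for study design reports an exenatide response rate near 60% and later unexpected dropout, so the final numbers may differ. The loss of information from dichotomising does not depend on any of these assumptions. A negative logistic result would be hard to interpret by itself, but it would not make aim 2 uninterpretable, because the trajectory analysis remains.

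**What to change.** Make the main aim-2 model a linear regression of the week 12-to-52 weight change, in kilograms or percent (one of them named in advance), on the metabolic parameters, adjusted for week-12 weight. Fit it in both groups as already planned. Keep the 1 kg logistic model and its c-statistic as a sensitivity analysis, with a sentence on why 1 kg was chosen.

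Do not replace 1 kg with a larger cut. At 3 kg, with mean loss 1 kg and SD 1.2 kg, 4.8% of 38 women gives 1.8 events. A further 5% of body weight is 4.5 kg at an assumed 90 kg. That gives about 0.07, 0.7 and 4 events among 38 for assumed mean losses of 1, 2 and 3 kg.

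The cost is a change of wording, using weights already collected. Results would be stated as weight change per unit of the parameter instead of odds ratios, and the c-statistic criterion would no longer govern the main aim-2 result.
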